#### 4.9.3. Vital Signs

Observed and changes from baseline (see Section 2.1.1) for vital signs assessment (weight, BMI, temperature, heart rate, respiratory rate, systolic blood pressure and diastolic blood pressure) will be summarized descriptively for the on-treatment period at the scheduled visit including re-allocated visits (EOT or unscheduled, see Section 2.3).

A shift table from baseline will be provided to summarize abnormalities at each scheduled visit, as well as for the worst post-baseline values during the on-treatment period. The determination of the worst post-baseline value will use the results from both scheduled and unscheduled visits. The abnormalities for vital sign parameters are described in Table 7 below.

**Table 7: Vital Sign Abnormal Ranges**

Vital Sign	Abnormal - Low	Normal	Abnormal - High
systolic blood pressure (mmHg)	< 90	90 - 140	> 140
diastolic blood pressure (mmHg)	< 60	60 - 90	> 90
heart rate (beats/min)	< 60	60 -100	>100
temperature (0C)	< 36	36 - 38	> 38
respiratory rate (beats/min)	< 12	12 - 18	> 18

All vital sign data by participant ID will be presented in a listing.

#### 4.9.4. ECG

Observed value and changes from baseline for ECG results (heart rate, PR interval, QRS duration, QT interval, and QTcF interval) will be summarized descriptively for the on-treatment period at the scheduled visits including re-allocated visits (EOT or unscheduled).

Morphic Therapeutic, Inc.  
Study Number: MORF-057-202

Statistical Analysis Plan  
Version 1.0, 16SEP2024

A shift table from baseline will be provided to summarize abnormalities for QTcF at each scheduled visit, as well as for the worst post-baseline values during the on-treatment period. The determination of the worst post-baseline value will use the results from both scheduled and unscheduled visits. QTcF > 450 ms among male participants and QTcF > 470 ms among female participants will be considered above normal ranges.

Overall interpretation with clinical significance will also be summarized at each scheduled visit.

All ECG data by participant ID will be presented in a listing.

#### 4.10. Pharmacokinetic Analysis

Plasma concentrations of MORF-057 will be summarized by treatment groups at scheduled visit and time using descriptive statistics including number of participants, mean with SD, median, CV% and geometric mean with CV% based on PK Population.

Mean concentrations at any individual time point will only be calculated if at least half of the participants have valid values (i.e., quantifiable, and not missing) at this time point. In cases where a mean value is not calculated, due to the above criterion not being met, the mean value will be set to missing.

The handling rules for values below limit of quantification (BLQ) are described in Section 2.7.1.

The PK analyses for the Induction Period will include the PK data collected during the 12-week Induction Period, see Section 1.5.1. The PK analyses for the 52-week Treatment Period will include the PK data collected during the 52-week Treatment Period, see Section 1.5.2. Additional PK and PK/PD analyses will be conducted as deemed appropriate and may be reported separately from the Clinical Study Report.

#### 4.11. Pharmacodynamic Analysis

Observed values and changes from baseline for  $\alpha 4\beta 7$  and  $\alpha 4\beta 1$  receptor occupancies will be summarized by treatment groups at scheduled visits using descriptive statistics including number of participants, mean with SD, median, CV% and geometric mean with CV%. The handling rules for PD data are described in Section 2.8.

Plot of mean with SD and boxplot for  $\alpha 4\beta 7$  and  $\alpha 4\beta 1$  receptor occupancies over scheduled visits will be provided.

The normalized relative expression level of human CCR9 mRNA in blood (relative to the pre-dose baseline) will be calculated at each timepoint using the lab-reported parameter CCR9\_IPO8\_DeltaCt (i.e., CCR9 Ct – IPO8 Ct), where the relative expression of CCR9 mRNA in blood at a given timepoint relative to pre-dose baseline is calculated using the following formula:

- Relative expression at timepoint x =  $2^{- (CCR9\_IPO8\_DeltaCt \text{ at timepoint x} - CCR9\_IPO8\_DeltaCt \text{ at baseline})}$

The CCR9 mRNA expression will be summarized by treatment groups at each timepoint using descriptive statistics.

The PD analyses for the Induction Period will include the PD data collected during the 12-week Induction Period, see Section 1.5.1. The PD analyses for the 52-week Treatment Period will include the PD data collected during the 52-week Treatment Period, see Section 1.5.2.

Morphic Therapeutic, Inc.  
Study Number: MORF-057-202

Statistical Analysis Plan  
Version 1.0, 16SEP2024

Additional analysis of PD endpoints may be described in a biomarker analysis plan separate from the study SAP and reported separately.

## 5. INTERIM ANALYSIS

The analysis of the 12-week Induction Period will be performed after all the participants have completed the Week 12 assessments or discontinued the study before the Week 12 assessment, as described in Section 1.5.1. The primary and secondary efficacy endpoints will be formally tested only once, specifically at the time of the Induction Period Analysis. When the Induction Period analysis is performed, an exploratory analysis for the 52-week Treatment Period may also be conducted for the subgroup of participants who have either completed their Week 52 assessments or discontinued the study by the time the last randomized participant completes their Week 12 assessments.

An independent DSMB will review participant safety data and monitor scientific integrity throughout the study. Details related to the DSMB will be clearly delineated in the DSMB Charter.

## 6. APPENDICES

### 6.1. Calculation of Stool Frequency and Rectal Bleeding Subscores

Stool frequency and rectal bleeding subscores at baseline and post-baseline visits will be calculated based on a reference date determined as follows:

- For baseline, the reference date is the randomization date.
- For post-baseline visits, the reference date is:
  - The earliest of the visit date recorded on eCRF form, the start date of bowel preparation (if performed), or the date of endoscopy procedure, if the endoscopy procedure is performed at the visit.
  - The visit date recorded on the eCRF If no endoscopy procedure is performed at the visit.

The calculation of stool frequency and rectal bleeding subscores will use the 3 most recent consecutive days of completed diary entries (both stool frequency and rectal bleeding data must be non-missing on the same day) within the past 7 days from the reference date. If 3 consecutive days of completed diary entries are not available, then use the 4 most recent nonconsecutive days of completed diary entries within the 7-day period prior to the reference date. If there are fewer than 3 consecutive days or 4 nonconsecutive days of completed diary entries available, then the subscores are set to missing.

In the calculations of stool frequency and rectal bleeding subscores at baseline, diaries collected on the following days within the 7-day period from the reference date will be excluded:

- Days of bowel preparation
- The day of endoscopy + 2 days

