#### **2.4.3. Handling of Missing Data in Efficacy Analysis**

For analysis of primary and secondary efficacy endpoints and other binary exploratory efficacy endpoints, missing endpoint data will be imputed using a nonresponder imputation (NRI) method, unless otherwise specified. Participants will be considered nonresponders for the NRI analysis if they have missing clinical efficacy data at a time point of interest.

For continuous exploratory efficacy endpoints expressed as change from baseline at Week 12, the primary analysis will use the analysis of covariance (ANCOVA) model for comparing MORF-057 group with the placebo group. Participants who have missing baseline value or the value at Week 12 will be excluded from the analysis. The details are described in Section [4.8.3](#).

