#### 4.8.3.4. Additional Exploratory Efficacy Analysis

Additional exploratory analysis will be performed for change from baseline to Week 12 in the mMCS score by using an analysis of covariance (ANCOVA) model with treatment and randomization stratification factors as factors and baseline values as a covariate. Any participant who was randomized under the wrong stratum by mistakes will be analyzed according to the actual stratum the participant belongs to. The least-squares means and standard errors with 95% CIs for both changes from baseline in each treatment group and differences between MORF-057 and placebo groups will be provided. P-values will also be calculated for the exploratory use. Participants who do not have the baseline value or the value at Week 12 will be excluded from the analysis. The change from baseline to Week 12 in the mMCS score will also be summarized descriptively for each treatment group by previous use of advanced therapy for UC (naïve vs experienced), by baseline MES score (<3 vs 3), and by baseline mMCS score ( $\leq 7$  or  $> 7$ ).

Summary statistics (mean and SD) for baseline value, observed values and changes from baseline at scheduled visits including re-allocated EOT visit (see Section 2.3) will be provided by treatment groups for the following additional continuous exploratory variables on observed cases:

- Stool frequency subscore
- Rectal bleeding subscore
- Partial mMCS

The summaries will be provided both for the overall population and for the subgroups by previous use of advanced therapy for UC (naïve vs experienced) and by baseline MES score (<3 vs 3). The summaries will be provided at each scheduled visit up to Week 12 visit in the Induction Period Analysis, up to Week 52 visit in the 52-week Treatment Period Analysis, and up to Week 104 visit in the 104-week Total Treatment Period Analysis. Line plots showing mean values ( $\pm$  SE) and mean changes from baseline ( $\pm$  SE) at each of the scheduled visits will also be presented by treatment groups, both for the overall population and for the subgroups.

For the histologic variables, i.e., RHI, NI, and continuous Geboes score, descriptive summaries will also be provided by treatment groups for change from baseline at Week 12 in the Induction Period Analysis,

for change from baseline at Week 52 in the 52-week Treatment Period Analysis, and for change from baseline at Week 104 in the 104-week Total Treatment Period Analysis.

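### The fixed 7-day baseline diary window in SAP Section 6.1 can leave stool frequency and rectal bleeding subscores impossible to compute, depending on when the endoscopy took place, and the SAP does not say what then serves as baseline.

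*SAP*

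**What the plan says.** Section 6.1 derives both diary subscores by counting back from a reference date. "For baseline, the reference date is the randomization date". The calculation "will use the 3 most recent consecutive days of completed diary entries" in the past 7 days. Failing that, "then use the 4 most recent nonconsecutive days of completed diary entries" found "within the 7-day period prior to the reference date". The rule ends: "If there are fewer than 3 consecutive days or 4 nonconsecutive days of completed diary entries available, then the subscores are set to missing".

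At baseline only, two sets of days are removed from that same 7-day period: days of bowel preparation, and "The day of endoscopy + 2 days". The section does not lengthen the window to make up for them. After baseline the reference date moves back to the earliest of the visit, the start of preparation and the endoscopy, so preparation and endoscopy do not use up the window.

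The baseline subscores feed several analyses:

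- Clinical response at Week 12 (Section 4.8.2) is the only secondary endpoint and part of the testing hierarchy in Section 4.8.6. It requires a fall from baseline mMCS.
- For binary endpoints, Section 2.4.3 says: "Participants will be considered nonresponders for the NRI analysis if they have missing clinical efficacy data at a time point of interest". Section 4.8.2 applies the same rule to any data needed to determine response status.
- For the ANCOVA of mMCS change, Section 4.8.3.4 says: "Participants who do not have the baseline value or the value at Week 12 will be excluded from the analysis".

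Section 2.1.2 defines the efficacy baseline as the latest non-missing assessment before randomization. Section 1.2 defines study disease as an mMCS of 5 to 9.

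**The concern.** The excluded days come out of a window that is barely long enough to absorb them. One preparation day, the endoscopy day and two further days take 4 of 7. If they fall in the middle, the 3 days left are split between the two ends of the window. Whether a baseline exists then depends on how the site timed the endoscopy relative to randomization, and not on whether the participant kept the diary.

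If a missing baseline is left as it stands, a participant who may have improved markedly cannot be a clinical responder. The same applies to symptomatic response, MCS response and partial MCS response (Table 2). The participant also leaves the mMCS ANCOVA and cannot be placed in the baseline mMCS subgroup of Section 4.8.4.

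An interval of a few days between endoscopy and randomization is plausible. Section 1.2 requires the MES to be confirmed by a central reader, and baseline MES is a stratification factor, so the reading has to be back before randomization.

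**Working it through.** The SAP gives no figure on this point. Its one design figure is 80% power with 70 per group for remission of 7% against 22% at two-sided alpha 0.10 (Section 1.3). That reproduces as 81.5%, with 68 per group needed, and does not depend on baseline scores.

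**Inputs from Section 6.1.** Day 0 is randomization. The window is 7 days, read first as -7 to -1. The score needs 3 consecutive completed days or, failing that, any 4.

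**Assumptions.** Preparation takes 0, 1 or 2 calendar days before the endoscopy day (the SAP gives no number). The endoscopy exclusion is read as that day plus the two following days. With endoscopy on day -k and p preparation days, days -k-p to -k+2 are removed.

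**Perfect diary, window -7 to -1, endoscopy on days 0 to -10:**

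| Preparation days | Days excluded | Endoscopy days that cannot be scored | Days left |
|---|---|---|---|
| 0 | 3 | none | – |
| 1 | 4 | -4 | -7, -6, -1 |
| 1 | 4 | -5 | -7, -2, -1 |
| 2 | 5 | -3 | -7, -6 |
| 2 | 5 | -4 | -7, -1 |
| 2 | 5 | -5 | -2, -1 |

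**Other readings of the text:**

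| Window | Endoscopy exclusion | 1 preparation day | 2 preparation days |
|---|---|---|---|
| -6 to 0 | day + 2 after | -3, -4 fail | -2, -3, -4 fail |
| -7 to 0 (8 days) | day + 2 after | none fail | -3, -4 fail |
| -7 to -1 | 2 days in all | none fail | -3, -4 fail |

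With no separate preparation day, nothing fails outright under any of these readings.

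**Imperfect diary.** Assume each day is completed independently with probability 0.9, with window -7 to -1 and no separate preparation day:

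- Endoscopy on -3 or -7 leaves 4 consecutive days. The score exists if all 4 are complete or only an end day is missed: 0.9^4 + 2 × 0.9^3 × 0.1 = 0.6561 + 0.1458 = 0.8019. Missing: 19.8%.
- Endoscopy on -4 or -6 leaves a run of 3 plus one isolated day. The run must be complete: 1 - 0.9^3 = 27.1% missing.
- Endoscopy on -5 leaves -7, -6, -2, -1. All 4 are needed: 1 - 0.9^4 = 34.4% missing.
- With no excluded day in the window, enumerating all 7-day patterns gives 0.24% missing.

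With one preparation day, the same calculation gives 27.1% missing at -3 or -6 and 19.8% at -2 or -7, besides the certain failures at -4 and -5.

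**Effect on clinical response.** Suppose a share f of each arm has no baseline and is set to non-response, and response does not depend on being affected. Each rate becomes (1 - f) times its value, and so does the difference. For illustration only, a 25-point difference becomes 25 × 0.95 = 23.8 points at f = 5% and 25 × 0.85 = 21.3 points at f = 15%. Neither f nor the 25 points comes from the SAP.

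**The case against.** A reader might infer that anyone with endoscopy 4 or 5 days before randomization is automatically a non-responder. The SAP does not support that, for three reasons.

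First, Section 2.1.2 takes the latest non-missing assessment before randomization, and entry required an mMCS of 5 to 9, which itself needs both diary subscores. Some score should therefore exist, and it may be meant to serve. This stands as a possibility. However, Section 6.1 gives one baseline reference date, defines no earlier subscore and sets the value to missing. The SAP does not say which section governs.

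Second, if eligibility used the same diary rule, a participant who could not be scored would not have been randomized, and the affected share could be zero. The eligibility scoring, the preparation schedule and the interval from endoscopy to randomization are not in the SAP, so this cannot be excluded.

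Third, outright failure needs a separate preparation day and particular readings of the window and of the two-day addition. This is correct, and the tables show it. But Section 6.1 words the look-back in three different ways without saying whether the randomization day counts, so the ambiguity is itself part of the problem. The fragility at imperfect completion does not need a separate preparation day.

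It is also fair that the loss does not favour an arm. The diary and endoscopy timing that decide it precede treatment.

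**Conclusion.** The point holds in a limited form. As written, Section 6.1 can make the baseline diary subscores impossible to compute with a complete diary: for endoscopy on days -4 and -5 with one separate preparation day, and on -3 to -5 with two, under a -7 to -1 window. Other readings move or remove these days. Short of outright failure, 20% to 34% of baselines are missing for endoscopy on days -3 to -7 at an assumed 90% independent completion and no separate preparation day.

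Non-response follows only if Section 2.1.2 supplies no earlier score, which the SAP leaves open. The effect is then a dilution by (1 - f) of clinical response and the other binary endpoints that need a baseline diary score, plus lost participants in the mMCS ANCOVA. The share f is unknown and may be small or nil. A reader might also infer damage to the primary endpoint. There is none, because clinical remission (Section 4.8.1) uses Week 12 values only. The SAP should still settle this before unblinding, because the choice of reading can decide responder status on a multiplicity-controlled endpoint.

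**What to change.** In Section 6.1:

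1. Define the baseline window as the 7 most recent non-excluded days before randomization, going back at most 14 calendar days. Keep the existing 3-consecutive or 4-nonconsecutive requirement, and treat days separated by excluded days as nonconsecutive. For endoscopy on days -1 to -12, this restores 7 usable days within 11 calendar days (one preparation day) or 12 (two).
2. State whether the randomization day belongs to the window, use one wording for it throughout, and say whether the endoscopy exclusion covers three days or two.
3. Reconcile Section 6.1 with Section 2.1.2: say which earlier score, if any, replaces a baseline that still cannot be computed, for example the score used for eligibility.

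The cost is a few sentences of SAP text and a small programming change. The downside is that some baselines use older diary days: up to 11 - 7 = 4 days older with one preparation day, 12 - 7 = 5 with two, and at most 14 - 7 = 7 under the cap. A baseline derived this way may also differ from the eligibility score. If that is unwelcome, item 3 alone closes the gap, provided the replacement score is defined.

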#### Rectal bleeding subscore

The rectal bleeding subscore will be calculated as:

- Take the average of the daily rectal bleeding subscores from the 3 most recent consecutive days or 4 most recent nonconsecutive days if 3 consecutive days of completed diary entries are not available, and then round to the nearest integer (decimal  $\geq 0.5$  will be rounded to the next highest integer; decimal  $< 0.5$  will be rounded to the current integer).

#### Stool frequency subscore

The stool frequency subscore will be calculated as:

1. Compute the daily subscore first as below:
  - 0 if (stool frequency from each diary submission – normal number of stools)  $\leq 0$
  - 1 if (stool frequency from each diary submission – normal number of stools) = 1 or 2
  - 2 if (stool frequency from each diary submission – normal number of stools) = 3 or 4
  - 3 if (stool frequency from each diary submission – normal number of stools)  $> 4$
2. Take the average of the daily stool frequency subscores from the 3 most recent consecutive days or 4 most recent nonconsecutive days if 3 consecutive days of completed diary entries are not

available, and then round to the nearest integer (decimal  $\geq 0.5$  will be rounded to the next highest integer; decimal  $< 0.5$  will be rounded to the current integer).

Where the normal number of stools are the values recorded in the UC History eCRF form

- The value for the question ‘On average, when in remission from UC, what was the normal number of stools the subject had in 24 hours?’, when ‘Has subject previously been in remission from UC?’ = ‘Yes’.
- The value for the question ‘On average, prior to developing Ulcerative Colitis symptoms or UC diagnosis, what was the normal number of stools the subject had in 24 hours?’, when ‘Has subject previously been in remission from UC?’ = ‘No’.

## 6.2. Determination of the Actual Treatment Groups for Safety Analysis

Enrolled participants will be randomized into 4 treatment groups ([Table 3](#)) and will receive the treatment kits corresponding to the treatment group that they were randomized to, as described in [Table 8](#) below.

During the Induction Period, participants will receive their study drug supplies in Morning Kits and Evening Kits. Each kit includes 2 bottles, each of which contains either MORF-057 or Placebo depending on the kit type. Participants should take 1 capsule from each morning bottle in the morning and take 1 capsule from each evening bottle in the evening for a total of 4 capsules per day.

During the Maintenance Period/Maintenance Extension Period, participants will receive Maintenance Kits with 1 morning bottle and 2 evening bottles. They should take 1 capsule from the morning bottle in the morning and take 1 capsule from each evening bottle in the evening for a total of 3 capsules per day.

**Table 8: Treatment Kit Types for Different Treatment Arm**

	Induction Period (12 weeks)					Maintenance Period (40 weeks) + Optional Maintenance Extension Period (52 weeks)		
	Treatment Description	AM Kit Type	AM kit Bottles	PM Kit Type	PM Kit Bottles	Treatment Description	Maintenance Kit Type	Kit Bottles
Group 1	200 mg BID	MORF-057 200 mg Morning Kit of 2 Bottles	2M	MORF-057 200 mg Evening Kit of 2 Bottles	2M	100 mg BID	MORF-057 100 mg BID Maintenance Kit of 3 bottles	AM: 1M PM: 1M1P
Group 2	100 mg BID	MORF-057 100 mg Morning Kit of 2 Bottles	1M1P	MORF-057 100 mg Evening Kit of 2 Bottles	1M1P	100 mg BID	MORF-057 100 mg BID Maintenance Kit of 3 bottles	AM: 1M PM: 1M1P
Group 3	100 mg QD - M	MORF-057 100 mg Morning Kit of 2 Bottles	1M1P	MORF-057 Placebo Evening Kit of 2 Bottles	2P	100 mg QD - M	MORF-057 100 mg QD Maintenance Kit of 3 bottles	AM: 1M PM: 2P
Group 4	Placebo	MORF-057 Placebo Morning Kit of 2 Bottles	2P	MORF-057 Placebo Evening Kit of 2 Bottles	2P	200 mg QD - E	MORF-057 200 mg QD Maintenance Kit of 3 bottles	AM: 1P PM: 2M

BID: twice a day; QD - M: once a day (morning); QD - E: once a day (evening).

**Kit Bottles:** 2M: 2 bottles containing MORF-057; 1M1P: 1 bottle containing MORF-057 and 1 bottle containing Placebo; 2P: 2 bottles containing Placebo; 1M: 1 bottle containing MORF-057

Morphic Therapeutic, Inc.  
Study Number: MORF-057-202

Statistical Analysis Plan  
Version 1.0, 16SEP2024

The actual treatment group that each participant will be included in during the 12-week Induction Period, the 40-week Maintenance Period, and the 52-week Maintenance Extension Period will be determined based on the algorithm described below.

